3.2 Intervention/Treatment procedures

Study Day 1: Consented participants come to STM Church. During *Study Day 1*, they will be asked to complete the *CRC Knowledge Survey*, watch three CRC educational videos in Spanish and subsequently complete the *Post Video CRC Knowledge Survey* in Spanish. Both surveys will be administered on paper form.

3.3 Follow- up procedures

Study Day 2: The participants return to STM Church 30 +/- 7 days after their participation in *Study Day 1*. During *Study Day 2*, they will complete the *30 Day Follow Up CRC Knowledge Survey* on paper form.

Study Day 3: A random subset of participants from *Study Days 1* and *2* will be invited to participate in qualitative one-on-one interviews aimed at identifying barriers preventing Latinos from participating in CCTs.

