Study Design	To achieve our goals, Spanish speaking Latino individuals will be recruited to participate in an educational intervention that will take place at STM Church. On Study Day 1, participants will be given the CRC Knowledge Survey in Spanish before watching three CRC educational videos. After watching the videos, participants will be given the Post Video CRC Knowledge Survey . After 30 +/- 7 days, participants will be asked to return to the Church for Study Day 2 in order to complete the 30 Day Follow Up CRC Knowledge Survey ,

consisting of the original survey plus an open-ended question regarding barriers to participation in CCTs. Subsequently, 20 participants will be invited to participate in one-on-one qualitative interviews aimed at gaining further insight on Latino-perceived barriers to CCT participation. (Study Day 3)

Subject Population

Participants should:

Key Criteria for Inclusion and Exclusion:

1. Self-identify as Hispanic/Latino.
2. Be Spanish speakers.
3. Be 18 years or older.

Participants will be excluded if they:

1. Do not identify as Hispanic/Latino.
 2. Are not Spanish speakers.
 3. Are younger than 18 years old.
-

Number Of Participants

60

Study Duration

Every participant’s involvement will require at least two and a half hours over a 4-month period (two hours to take the *CRC Knowledge Survey*, watch the videos and take the *Post Video CRC Knowledge Survey* and thirty minutes to complete the *30 Day Follow Up CRC Knowledge Survey*). Participants willing to take part in a qualitative one-on-one interview will be asked to participate for an additional hour, totaling three and a half hours over a 6-month period. The entire study is expected to last 12 months.

Study Phases

A. Educational Video:

A. Educational Video

i. Screening

(i) Screening: Spanish speaking attendees at STM Church will be screened for study eligibility.

ii. Study Intervention

(ii) Intervention (Study Day 1): Consented participants will complete the *CRC Knowledge Survey*, watch three CRC educational videos and complete the *Post Video CRC Knowledge Survey*. Both surveys will be administered on paper form.

iii. Follow-Up

B. Identification of Barriers Preventing Latinos from participating in CCTs

(ii) Follow up (Study Day 2): In order to assess retention of knowledge, participants will return to STM Church 30 +/- 7 days after Study Day 1 to complete the *30 Day Follow Up CRC Knowledge Survey* on paper form.

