B. Identification of Barriers for Latino Participation in CCTs:

(Study Day 3): 20 of the participants will be asked to participate in a qualitative one-on-one interview aimed at identifying barriers preventing Latinos from participating in CCTs.

Efficacy Evaluations

Participants’ knowledge on CRC symptoms, risk factors, and general CRC facts will be assessed using questions from the “Bowel Cancer Awareness Measure” and from the “Colorectal Cancer Screening Decision Quality Instrument (CRC-DQI)”.

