2.2 Study Duration, Enrollment and Number of Participants

Participant commitment will consist of at least two and a half hours over a 4-month period (two hours to take the *CRC Knowledge Survey*, watch the videos and take the *Post Video CRC Knowledge Survey* and thirty minutes to complete the *30 Day Follow Up CRC Knowledge Survey*). Participants willing to take part in a qualitative one-on-one interview will commit an additional hour, totaling three and a half hours over a 6-month period. The entire study is expected to last 12 months. We intend to enroll a total of 60 participants. However, in order to recruit the necessary 20 for the qualitative interview, we may need to enroll more than 60 since not everyone participating in *Study Days 1 and 2* will choose to participate in *Study Day 3*.

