3.4 Subject Completion/ Withdrawal procedures

At the completion of *Study Day 2*, participants will receive a \$100 gift card and a study T-shirt from either our research assistant or one of the volunteers, all of whom will be Tango trained and enlisted on the study's IRB. Participants interested in participating in qualitative one-on-one interviews aimed at identifying barriers preventing Latinos from participating in CCTs will be invited to participate in *Study Day 3*. Following completion of *Study Day 3*, these participants will receive an additional \$50 gift card for their participation in the qualitative one-on-one interviews. Participants choosing to withdraw from the study may do so at any point by notifying the PI via email.

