4.5 Sample Size and Power

A traditional “power analysis” is not directly applicable to the primary endpoint of the study which is qualitative in nature. Based on published methodologies to assess the adequate sample to reach “saturation”,⁵²⁻⁵⁴ we chose to invite 20 participants for qualitative interviews.

For our quantitative, secondary endpoints, a traditional “power analysis” was performed. A total of 60 participants will be recruited into the study. If in our study population the mean difference is 0.4, which as defined by Cohen is a small to medium difference, and the pre- to post- correlation is 0.5, then the power to reject the null hypothesis will be over 80%. If the differences in our study population are more extreme, our sample size will have even more power to reject the null hypothesis.

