8. DATA COLLECTION AND MANAGEMENT

Every participant will be assigned a unique deidentified study number upon enrollment. When a participant arrives at STM Church and before they get seated, members of the study team will verify their name and DOB and subsequently enter their unique deidentified study number on their survey form.

At the beginning of *Study Day 1*, members of the study team will distribute paper surveys with deidentified study numbers to the corresponding participants pre- and post-video projection. In order to ensure privacy, adequate seating space between participant will be created. Upon completion of the surveys, members of the study team will perform a visual review of the survey to identify any quality control items such as illegible responses or stray marks across response bubbles. All completed surveys

with a corresponding unique, deidentified study number will be placed into a portable file tote to assure privacy. Within 72 hours of collection, pre- and post-video survey responses for each participant will be uploaded to REDCap. Paper surveys will be stored in a secure file cabinet in the PI's academic office. Similar procedures will be followed for the paper surveys collected during *Study Day 2*.

On *Study Day 3* (one-on-one qualitative interview), the audio of the interview will be recorded using a recording device and transcribed by GMR Transcription. ATLAS.ti software will be used for the analysis of the 20 deidentified transcripts. The deidentified transcripts will be stored in a secure file cabinet in the PI's academic office.

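### Does the loose wording on how the 20 interviewees are chosen, and on what 20 counts, leave the primary endpoint undefined?

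*Combined protocol and SAP*

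**What the plan says.** **Who is invited.** Section 3.3 (Study Day 3) invites "A random subset of participants from" Study Days 1 and 2. Section 3.4 reads "Participants interested in participating in qualitative one-on-one interviews aimed at identifying barriers preventing Latinos from participating in CCTs will be invited" to Study Day 3. Section 2.2 and the synopsis (Study Duration) refer to those willing to take part.

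**What 20 counts.** In the synopsis (Study Design), "20 participants will be invited to participate in one-on-one qualitative interviews"; under Study Phases, "20 of the participants will be asked to participate in a qualitative one-on-one interview". Section 4.5, citing literature on saturation, says "we chose to invite 20 participants for qualitative interviews". By contrast, section 2.1 has 20 of the 60 taking part in an interview, section 4.4 has twenty enrolled participants interviewed, and section 8 states "ATLAS.ti software will be used for the analysis of the 20 deidentified transcripts".

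**What happens if too few agree.** Section 2.2 gives 60 as the intended enrolment and then adds a contingency: "in order to recruit the necessary 20 for the qualitative interview, we may need to enroll more than 60 since not everyone participating in" the first two study days is expected to go on to the interview. Section 4.5 says "A total of 60 participants will be recruited into the study" and does not repeat the exception.

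**The concern.** The interviews supply the primary endpoint, and section 4.4 reports themes as a percentage of participants. With 20 interviewees each person counts for 100/20 = 5 percentage points, so a reader will want to know how they were picked. A random draw and self-nomination are different sampling schemes, and each has a sentence in the protocol to support it.

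Twenty invited equals twenty interviewed only if nobody declines, and section 2.2 expects some to decline. The same section names additional enrolment as the remedy, without first mentioning participants not yet invited. Taken literally, the study team could invite 20, fall short, and enrol new people while about 40 existing participants were never asked. Each new person would give at least two and a half hours and receive a $100 gift card. If fewer than 20 of the 60 were willing, everyone willing would be interviewed and the word random would no longer fit.

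**Working it through.** **The plan's own figure.** The 20 comes from cited saturation literature, not from a formula, so there is nothing to recompute. The check is a comparison of the text, followed by a calculation of how much the order of invitation matters.

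**Step 1: selection.** Section 3.3 says how invitations are spread. Section 3.4 deals with completion, gift cards and withdrawal, and its reference to interest reflects that the interview is voluntary. A random draw among volunteers satisfies both sections. No sentence says this outright, but neither section excludes the other.

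**Step 2: the meaning of 20.** Sections 2.1, 4.4 and 8 count people interviewed or transcripts. Section 2.2 calls 20 necessary and expects decliners, which makes sense only if 20 is the number completed. The invited or asked wording in the synopsis and section 4.5 is looser phrasing of the same target.

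**Step 3: the order.** Section 2.2's reason for exceeding 60 is that some of those in Study Days 1 and 2 will not continue. The pool it describes is all of those participants, not the first 20 drawn. A shortfall in that pool presupposes that the pool was approached.

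**Step 4: size.** Let *a* be the acceptance rate and *n* the number returning for Study Day 2. The documents give neither, so both are assumptions; *n* = 45 is 75% of 60.

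*Literal reading (invite 20, then enrol new people).*
- P(fewer than 20 interviews from 20 invitations) = 1 − a²⁰: 87.8% at a = 0.9, 98.8% at 0.8, over 99.9% at 0.6.
- Extra enrolment, with every new person invited, = 20(1 − a)/a: 2.2, 5.0 and 13.3. Dividing by 0.75 for return to Study Day 2 gives 3.0, 6.7 and 17.8.

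*Natural reading (existing participants first).* The chance of needing more than 60 is P(Binomial(n, a) ≤ 19):

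| Acceptance *a* | *n* = 60 | *n* = 45 |
|---|---|---|
| 0.9 | < 0.001% | < 0.001% |
| 0.8 | < 0.001% | < 0.001% |
| 0.6 | < 0.001% | 1.2% |
| 0.5 | 0.3% | 18.6% |
| 0.4 | 11.7% | 67.9% |

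The mean number of invitations needed is 20/a: about 22, 25 and 33 at a = 0.9, 0.8 and 0.6, all within the 45 or 60 assumed to return. On average 20 interviews are reached if a is at least 20/60 = 33% with 60 returning, or 20/45 = 44% with 45.

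**Step 5: effect on the secondary endpoints.** Section 4.5 claims over 80% power with 60 participants. With a standardised difference of 0.4 and a correlation of 0.5, the paired effect is 0.4/√(2(1 − 0.5)) = 0.40. A two-sided 5% paired t-test (level assumed; section 4.5 does not state it) then has 86.2% power at 60. Enrolling more than 60 can only raise this.

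**The case for a change.** The strongest argument for a change is that the protocol itself chose the word random, yet gives no sampling frame and no method of drawing. On one reading a report could describe the interviewees as a random subset, on another as interested volunteers, and both could be traced to the text. At 90% acceptance or less, 20 invitations will probably not yield 20 interviews, so some form of replacement is likely to be needed, and section 2.2 names only new enrolment. Section 4.5 also attaches the saturation argument to the number invited, although saturation depends on interviews held.

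All of that is accurate as a description of the wording. What does not stand is the consequence. The figures of 88% to over 99.9%, and of 2 to 18 extra participants, describe a team that recruits strangers while leaving about 40 enrolled people unasked; no section directs this. Nor is a report prevented from saying how people were chosen: the investigators can give the numbers invited, accepting and declining, and keep the word random for a draw that was actually made. Section 2.2 says that more than 60 may be needed; this is a contingency, not a forecast that fewer than 20 of the 60 will agree.

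**Conclusion.** The inconsistencies in wording are real, but they are a gap that a sensible team fills from the document itself. Twenty means completed interviews, interviewees are volunteers under either wording, and enrolment above 60 is a fallback once the existing participants have been approached. On that reading the fallback is unlikely to be used: below 0.001% with 60 returning and at most 1.2% with 45, at assumed acceptance of 60% to 90%. It becomes a live possibility only at lower acceptance (12% with 60 returning and 68% with 45, at 40%), and that is the situation section 2.2 provides for.

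The conclusion rests on reading section 2.2's reason for exceeding 60 as covering all Study Day 1 and 2 participants, and on acceptance and return rates that the documents do not supply. Whichever order is used, no effect on the themes is shown, the analysis in section 4.4 is unchanged, and power for the secondary endpoints is not reduced. No change to the plan follows.

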3.4 Subject Completion/ Withdrawal procedures

At the completion of *Study Day 2*, participants will receive a \$100 gift card and a study T-shirt from either our research assistant or one of the volunteers, all of whom will be Tango trained and enlisted on the study's IRB. Participants interested in participating in qualitative one-on-one interviews aimed at identifying barriers preventing Latinos from participating in CCTs will be invited to participate in *Study Day 3*. Following completion of *Study Day 3*, these participants will receive an additional \$50 gift card for their participation in the qualitative one-on-one interviews. Participants choosing to withdraw from the study may do so at any point by notifying the PI via email.

3.5 Screen failure procedures

At the beginning of each educational session, eligibility requirements (age \geq 18 years of age; identifying as Hispanic/Latino and being Spanish speaker) will be confirmed for each registered individual. In the unlikely event that an ineligible individual had been registered, this will be noted and the involved parties reminded of the eligibility requirements and their inability to participate in the study.

4 STUDY EVALUATIONS AND MEASUREMENTS

4.1 Efficacy Evaluation

To assess the impact of the CRC educational videos in Spanish on participant's knowledge of CRC symptoms, risk factors, screening, and facts, this study will utilize questions obtained from 3 subscales from 2 questionnaires previously validated in English.

1. Participants' knowledge on CRC symptoms will be assessed using the "Knowledge of Warning Signs" questions from the "Bowel Cancer Awareness Measure". Potential answers to these questions include "Yes", "No" and "Don't Know". The overall score will range from 0 to 9 and it is anticipated that average scores will increase after the intervention. Higher scores imply greater knowledge of symptoms.
2. Participant's knowledge on CRC risk factors will be assessed using the "Knowledge of Risk Factors" questions from the "Bowel Cancer Awareness Measure". This scale is measured using a Likert 1-5 scale with "1" corresponding to "Strongly Disagree" and "5" corresponding to "Strongly Agree". The overall score will range from 11 to 55 and it is anticipated that the average scores will increase after the intervention. Higher scores imply greater knowledge of risk factors.
3. Participant's knowledge on CRC screening and general facts will be assessed using nine questions from the "Colorectal Cancer Screening Decision Quality Instrument (CRC-DQI)". The overall score will range from 0 to 9 and it is anticipated that average scores will increase after the intervention. Higher scores imply greater knowledge of general facts.

STATISTICAL CONSIDERATIONS

4.2 Primary Endpoint

Identify novel Latino-perceived barriers to participation in CCTs.

4.3 Secondary Endpoints

The Secondary Endpoints of our study are to assess the association of:

1. Educational videos on knowledge of CRC symptoms.
2. Educational videos on knowledge of CRC risk factors.
3. Educational videos on knowledge on CRC screening and facts.
4. Watching the videos and willingness to participate in CCTs.

4.4 Methods

Primary Endpoint: Twenty enrolled participants will participate in qualitative, semi-structured, one-on-one interviews that will be performed in Spanish. The interviews will be recorded and transcribed.

ATLAS.ti software will be used for the transcript analysis. The top 2 conceptual themes within each section of the interview (attitudes regarding general clinical trials, attitudes regarding CCTs, and perception of the Hispanic/Latino community) and the top 3 higher-level, holistic themes across the sections will be reported in terms of percentage of participants.

Secondary Endpoint 1: Use of repeated measures ANOVA with appropriate follow-up contrasts to compare total number of correct responses within three time points (baseline vs post-video; baseline vs 30 +/- 7 days follow-up; post-video vs 30 +/- 7 days follow-up) accounting for multiple observations within participants. Knowledge pertaining to CRC symptoms will be assessed using the “Knowledge of Warning Signs” questions from the “Bowel Cancer Awareness Measure”. Potential answers include “Yes”, “No” and “Don’t Know”. The overall score will range from 0 to 9 and it is anticipated that average scores will increase after the intervention. Higher scores imply a greater knowledge of symptoms.

Secondary Endpoint 2: Use of repeated measures ANOVA with appropriate follow-up contrasts to compare total number of correct responses within three time points (baseline vs post-video; baseline vs 30 +/- 7 days follow-up; post-video vs 30 +/- 7 days follow-up) accounting for multiple observations within participants. Knowledge pertaining to CRC risk factors will be assessed using the “Knowledge of Risk Factors” questions from the “Bowel Cancer Awareness Measure”. This scale is measured using a Likert 1-5 scale with “1” corresponding to “Strongly Disagree” and “5” corresponding to “Strongly Agree”. The overall score will range from 11 to 55 and it is anticipated that the average scores will increase after the intervention. Higher scores imply higher knowledge of risk factors.

Secondary Endpoint 3: Use of repeated measures ANOVA with appropriate follow-up contrasts to compare total number of correct responses within three time points (baseline vs post-video; baseline vs 30 +/- 7 days follow-up; post-video vs 30 +/- 7 days follow-up) accounting for multiple observations within participants. Knowledge of CRC screening and general facts will be assessed using nine questions from the “Colorectal Cancer Decision Quality Instrument (CRC-DQI)”. The overall score will range from 0 to 9 and it is anticipated that average scores will increase after the intervention. Higher scores imply greater knowledge of screening and facts.

Secondary Endpoint 4: Since questionnaires will be completed pre and post video, we will explore, in a preliminary fashion, the association between watching the video (X) and willingness to participate in CCTs (Y) using repeated-measures/mixed-effects logistic regression on the paired responses of participants. The mediating effect of *Study Day 1* post-video health knowledge levels (M) on the relationship between X and Y (established in the preliminary step above) will be explored. Using a structural equation modeling approach, two mixed-effects generalized linear models will be carried out: one model uses both X and M to predict Y, while another uses only X to predict M. The two

models will be compared and tested using the algorithm introduced by Imai and colleagues^{50,51} The estimated average causal mediation effect (from X to Y, through M) will be tested using the bootstrapping method with 1,000 replications, and the proportion of the effect being mediated will be reported as the effect size. Lastly, in order to explore an adjusted approach, the same steps used for the mediation model will be replicated, while incorporating demographic variables as covariates.

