
Safety Evaluations
 <hr/> 
Statistical And Analytic Plan
	
N/A, this study imposes minimal risk.
 <hr/> 
A. Identification of Barriers: The top 2 conceptual themes within each section of the interview (attitudes regarding general clinical trials, attitudes regarding CCTs, and perception of the Hispanic/Latino community) and the top 3 higher-level, holistic themes across the sections will be reported in terms of percentage of participants.
 
B. Assessment of the potential impact of the educational videos in Spanish on CRC knowledge: Use of repeated measures ANOVA with appropriate follow-up contrasts to compare total number of correct responses within three time points (baseline vs post-video; baseline vs 30 +/- 7 days follow up; post-video vs 30 +/- 7 days follow-up) accounting for multiple observations within participants.
 
C. Exploration of the potential relationship between an increase in health knowledge of a specific cancer via educational videos in Spanish and willingness to participate in CCTs: Since questionnaires will be completed pre- and post-video, we will explore, in a preliminary fashion, the association between watching the video (X) and willingness to participate in CCTs (Y) using repeated-measures/mixed-effects logistic regression on the paired responses of participants. The mediating effect of Study Day 1 post-video health knowledge levels (M) on the relationship between X and Y (established in the preliminary step above) will be explored. Using a structural equation modeling approach, two mixed-effects generalized linear models will be carried out: one model uses both X and M to predict Y, while another uses only X to predict M. The two models will be compared and tested using the algorithm introduced by Imai and colleagues. The estimated average causal mediation effect (from X to Y, through M) will be tested using the bootstrapping method with 1,000 replications, and the proportion of the effect being mediated will be reported as the effect size. Lastly, in order to explore an adjusted approach, the same steps used for the mediation model will be replicated, while incorporating demographic variables as covariates.

--	---

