increase willingness to participate in CRC screening,⁴³ we anticipate it could similarly increase willingness to participate in CCTs. This can be achieved by increasing awareness of CRC and its treatment options ultimately leading to improved decision-making.²⁷

Questionnaire: Knowledge on CRC and willingness to participate in CCTs will be assessed using 3 subscales from 2 CRC knowledge questionnaires previously validated in English. [name] and [name] from the Odum Institute combined the 3 subscales^{44–46} to form our Pilot Study Questionnaire. This Pilot Study Questionnaire has been translated into Spanish by Language Line Solutions, hired through the UNC Clinical Research Support Office (CRSO), and revised, using an iterative process with input from the LCRB, for linguistic and cultural relevance and accuracy. The resultant Pilot Study Questionnaire consists of 29 items that assess health knowledge levels and 1 that assesses willingness to participate in CCTs (30 total questions). General knowledge on CRC will be assessed using the prompted 9-item “Awareness of warning signs” (Yes/No) and the prompted 11-item “Awareness of risk factors” (5 point Likert agreement scale) subscales of the “Bowel/CRC Cancer Awareness Measure (Bowel/CRC CAM)”.⁴⁵ Specific knowledge on CRC screening will be assessed using the 9-item “Knowledge on CRC screening” (mixed types of response options) subscale from the CRC Screening Decision Quality Instrument (CRC-DQI).⁴⁶ Our outcome variable, *willingness to participate in CCTs*, will be assessed using a “Yes/No” item.^{28,36,42} Our Pilot Study Questionnaire is used in all three surveys, namely the *CRC Knowledge Survey; Post Video CRC Knowledge Survey and 30 Day Follow Up CRC Knowledge Survey*. Additionally, the *CRC Knowledge Survey*, administered pre-video, includes seventeen questions capturing demographic information (47 total questions), while the *30 Day Follow Up CRC Knowledge Survey* contains in addition to the pilot study Questionnaire, an open-ended question aimed at capturing barriers preventing Latinos from participating in CCTs (31 total questions).

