1 STUDY OBJECTIVES

1.4 Primary Objective

The Primary Objective of this study is to identify novel Latino-perceived barriers to participation in CCTs.

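### The primary reporting rule is not restricted to barriers, although barriers are the primary endpoint

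*Combined protocol and SAP*

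**What the plan says.** The objective and the endpoint agree. Under Study Objectives: "The Primary Objective of this study is to identify novel Latino-perceived barriers to participation in CCTs". Section 4.2 gives the primary endpoint as "Identify novel Latino-perceived barriers to participation in CCTs".

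Section 4.4 gives the only analysis for that endpoint. Twenty interviews are held, recorded, transcribed and analysed in ATLAS.ti. The report then contains two sets of themes:

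- "The top 2 conceptual themes within each section of the interview", where the sections are "attitudes regarding general clinical trials, attitudes regarding CCTs, and perception of the Hispanic/Latino community";
- "the top 3 higher-level, holistic themes across the sections will be reported in terms of percentage of participants".

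The synopsis repeats the rule under a label that does mention barriers: "Identification of Barriers : The top 2 conceptual themes within each section of the interview". Section 3.3 describes the interviews as "qualitative one-on-one interviews aimed at identifying barriers preventing Latinos from participating in CCTs".

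The 30-day survey also carries "an open-ended question aimed at capturing barriers preventing Latinos from participating in CCTs (31 total questions", but section 4.4 assigns no analysis to it.

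**The concern.** The endpoint names one kind of content, barriers, while the rule selects on another property, how prominent a theme is within a section. Neither section 4.4 nor the synopsis defines a barrier, separates barriers from facilitators or neutral views, or says that only barriers are ranked.

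Since only two themes per section survive, the order of the themes decides what is reported. If a favourable or neutral theme is raised by more interviewees than a barrier, it takes the place, and a barrier named by several people may not appear in the primary result. Section 4.4 has no second route by which it would reappear. If someone decides after coding which of the reported themes count as barriers, that judgement is made with the results in view.

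**Working it through.** **No figure of the plan's own to reproduce.** Section 4.5 states that a power analysis does not apply to the primary endpoint and bases the 20 interviews on saturation. Its power statement concerns the secondary endpoints and does not bear on this point.

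**Step 1: count what the rule reports.**

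| Source | Themes reported | Required to be barriers |
|---|---|---|
| General clinical trials section | 2 | 0 |
| CCT section | 2 | 0 |
| Community perception section | 2 | 0 |
| Across sections | 3 | 0 |
| Total | 3 × 2 + 3 = 9 | 0 |

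Under the rule as written, the number of barriers reported can be anything from 0 to 9. This step needs no assumption.

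**Step 2: illustrate how often a section would show no barrier.** The documents give no theme prevalences, so these inputs are assumptions, apart from the 20 interviews and the two places per section:

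- each section has four barrier and four non-barrier themes;
- non-barrier themes have prevalences of 60, 50, 40 and 30%;
- barrier themes have the same four values, shifted by −20 to +20 points;
- themes are mentioned independently, and the leading themes are those mentioned by most interviewees, which fits reporting as a percentage of participants.

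For theme j, the number of interviewees mentioning it is X_j ~ Binomial(20, p_j). The two largest X_j are reported, with ties broken at random. P0 is the probability that neither is a barrier, found by simulation with at least 200,000 draws per row.

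| Barrier themes relative to non-barrier themes | Barrier prevalences (%) | P0 per section |
|---|---|---|
| 20 points more common | 80, 70, 60, 50 | 0.2% |
| 10 points more common | 70, 60, 50, 40 | 3% |
| Equally common | 60, 50, 40, 30 | 15% |
| 10 points less common | 50, 40, 30, 20 | 42% |
| 20 points less common | 40, 30, 20, 10 | 74% |

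**Step 3: from one section to all three.** In the equal case the probabilities of 0, 1 and 2 barriers in a section are 0.15, 0.70 and 0.15. The expected number is 0.70 × 1 + 0.15 × 2 = 1.0 per section, or 3 of the 6 section places. If the sections are also taken as independent, the chance that all six places hold no barrier is P0 cubed:

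- equally common: 0.15³ = 0.003, about 0.3%;
- 10 points less common: 0.424³ = 0.076, about 8%;
- 20 points less common: 0.74³ = 0.405, about 41%.

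The three cross-section themes were not modelled.

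**The case against.** The strongest reply is that the rule should be read in its setting. It stands under the primary endpoint, which is defined as barriers. The synopsis labels it as identifying barriers, and the interviews are repeatedly described as directed at barriers. The words quoted from section 4.4 are section names: they say where in the interview a theme arises, not what kind of theme it is. Fear, mistrust or lack of family support voiced under an attitudes section is itself a perceived barrier.

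Most of this stands. A reader might infer that the plan analyses attitudes instead of barriers, or that the primary result will consist mainly of non-barriers. The documents support neither reading. The interview guide and codebook are not in the text available, so barrier prompts within each section cannot be excluded. With barrier-directed questions, barrier themes may well be the more common ones, and then a section with no barrier is rare (3% or less in the rows above).

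Nor does the choice of interviewees settle the matter. They come from people who took part in Study Days 1 and 2, but joining a church-based survey does not show a favourable view of cancer trials.

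What remains is narrower. Labels and aims state an intent, and prompts affect what is collected. Neither decides which themes are ranked and reported. If some attitudes are barriers and others are not, the plan needs a rule to tell them apart, and it has none.

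**Conclusion.** The concern holds in a limited form: the primary reporting rule is not restricted to barriers. None of its 9 places has to hold one, and the cut at two per section can drop a barrier in favour of a more common favourable or neutral theme. The result will probably include some barriers.

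The structural finding rests on the text alone. The size does not. Between about 0% and 74% of sections would report no barrier, as barrier themes go from 20 points more common to 20 points less common than non-barrier themes. That range is driven wholly by the assumed prevalences and is not a forecast. It is also a per-section figure: a primary result with no barrier in any section place is much less likely, at about 0.3% in the equal case.

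The change should be made because this is the primary endpoint and the remedy is small. Whether a reported barrier is novel is a separate question, not settled here.

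**What to change.** Change section 4.4 and the synopsis in the same way:

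1. Before ranking, code every theme as barrier, facilitator or neutral, using short definitions written before coding starts.
2. For the primary endpoint, rank and report barrier themes only, per section and overall, each as n of the number interviewed.
3. Report facilitator and neutral themes separately, as descriptive context.

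Tagging each barrier as patient, physician or healthcare-system level, the levels named in the rationale, is optional.

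The cost is one extra code attribute in ATLAS.ti, which is already planned, and a wording change in two places. No further interviews are needed. The change should precede coding, so that what counts as a barrier is not decided after the themes are known.
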